9 SAFETY AND ADVERSE EVENTS

All AEs occurring during the study, including those not meeting the criteria of an Unanticipated Adverse Device Effect (UADE) will be recorded on the appropriate case report form. Records of these events will be maintained, and reports will be submitted to the FDA and IRB according to the regulatory requirements. Expected clinical AEs and nonsignificant (not serious) clinical AEs will not be reported.

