- Placement of a lead in the epidural space is a surgical procedure that may expose the patient to risks of epidural hemorrhage, hematoma, infection, spinal cord compression, and/or paralysis.
- Radicular chest wall stimulation.
- Cerebrospinal fluid (CSF) leakage.
- Persistent pain at the electrode site or receiver site.
- Seroma at the incision site, as well as serosanguinous drainage.
- Implant migration.
- Allergic or rejection response to implant materials.
- Lead migration and/or local skin erosion.
- Paralysis, weakness, clumsiness, numbness, or pain below the level of implantation.

Risks associated with ES following implantation:

Hardware malfunction, discomfort, or abdominal tightness during ES, increased or decreased spasticity, bowel or bladder incontinence, shortness of breath, muscle soreness, or fatigue may occur during ES. Autonomic dysreflexia is a risk for those with mid-thoracic or higher-level injuries.

Risks associated with MRI

Dislodgement of some metal implants and claustrophobia may occur during MRI. Subjects will be rigorously screened in the same fashion as clinical patient by MRI technicians prior to each scan. Earplugs will also be provided to keep MRI noise within a safe audible range. Due to the potential for tissue heating, image artifacts, induced voltages in the neurostimulator or leads, and lead dislodgement, MRIs will not be obtained after epidural stimulator implantation.

Risks associated with Transcranial magnetic stimulation

Transcranial magnetic stimulation is electrical pulses from the magnet to the brain. Risks are possible hearing changes, headache, and a chance of heating on the skull where the magnet is placed.

Risks associated with electromyography and electroneurography

Risks involved with EMG include skin irritation or allergic reaction from the adhesive used to apply sensors. Additionally, electroneurography carries the risk of pain and discomfort from needle placement, and infection at the needle stick site.

Risks associated with urodynamic studies

Urodynamic studies may carry the risk of autonomic dysreflexia, mild irritation of the urethra, and infection.

Steps taken to minimize the occurrence and severity of associated risks:

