Trained study staff and medical technicians will directly oversee all tasks. Body weight support, a safety gait belt, and other safety measures as necessary will be utilized to lessen the risks involved with rehabilitation and weight-bearing tasks. Transcutaneous electrode sites will be checked routinely throughout rehabilitation sessions, and if skin irritation or damage is observed, no further stimulation will occur until the site has healed. To mitigate risks in general, the protocol will be conducted as stated, medical professionals will be consulted, and care will be provided to address any study-related concerns that arise. All members of the research team will be trained to identify the occurrence of risks related to this study. If risk occurrence is observed, study-related activities will be halted until appropriate medical care is given and it is deemed safe for the subject to continue study-related activities. Because the interventions have been used for individuals with spinal cord injury and subjects will have been carefully screened, we do not anticipate any serious adverse events in this study. However, if they do occur, serious adverse events will be reported to the PI, medical monitor, IRB, and FDA within the appropriate reporting timeframes. Adverse events will be reported to the PI, the site medical monitors IRB, and FDA within the appropriate reporting timeframes.

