3.4 Primary Safety Endpoints

Primary safety endpoints of the study will be oriented to adverse events that could originate from the implantation of the ES electrodes, or the operation of either neurostimulator device as well as to those that could arise from performing the locomotor rehabilitation sessions. Patients will be asked to report any discomfort that they encounter throughout the study. A detailed selection of the candidates by the Principal Investigators and the study team will be crucial to select individuals who fit the inclusion criteria of the study, minimizing risk for potential adverse events throughout the study. Subjects will undergo a screening phase oriented to identify conditions that could potentially represent a higher than the expected risk for conducting this study.

To visualize electrode positioning of the ES neurostimulator system, fluoroscopy and spine computed tomography will be performed. To limit adverse events that could result from operating the neurostimulator device, stimulation parameters will be selected within safe ranges as provided by the manufacturer's specifications of ES pulse generators. Specifically, we will deliver stimulation within the following ranges:

ES parameters: pulse width 50-1000 microseconds; frequency 0.5-200 Hz; amplitude 0-25.5 mA

The procedure to connect the externalized ends of the percutaneous electrodes (model 3086) to the Ripple NOMAD will consist of minimizing strain on the connections by creating loops in the externalized lead wires and lead extensions (model 3386). The loops will be positioned in proximity to the implant site using adhesive tape. Additionally, each connection will be secured using adhesive tape. Finally, each connection and implantation site, as well as the strain relief loops, will be protected using an adhesive bandage.

During sessions of rehabilitation with stimulation, the looped lead wires and lead extensions will be connected to Abbott's battery-powered pulse generator (model 3599) via "multilead trial cables" (model 3013). Stimulation waveforms and electrode configurations will be transmitted wirelessly from the "clinician programmer" (model 3874) to the battery powered pulse generator. The battery-powered pulse generator, multilead trial cables, and clinician programmer are manufactured by Abbott for use with their ES system.

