9.7.3 Related

A problem or event is "related" if it is possibly related to the research procedures.

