9.13 AE reporting

When an AE has been identified, the PI will take appropriate action to protect the participant and then complete the Study Adverse Event Worksheet and log. The PI will evaluate the AE and determine the necessary follow-up and reporting required. Then, the PI will promptly review documented UADE and report the results to the FDA within 10 working days and the Mayo Clinic's IRB within 5 working days Thereafter, the PI will submit additional reports as requested.

Additionally, information related to the AE will be recorded on CRFs and within the research database. The PI will review all AE reports to determine if specific reports need to be made to the IRB and FDA. The PI will sign and date the AE report when it is reviewed. For this protocol, only directly related SAEs/UPIRTSOs will be reported to the IRB.

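### Section 9 exempts expected adverse events from reporting with no seriousness limit, which covers serious implant complications listed as anticipated risks and conflicts with the protocol's other reporting rules

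*Combined protocol and SAP*

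**What the plan says.** Section 9 opens by requiring every adverse event to be recorded on the case report form. It then says that "reports will be submitted to the FDA and IRB according to the regulatory requirements", and follows this with "Expected clinical AEs and nonsignificant (not serious) clinical AEs will not be reported".

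Section 1.4.2, headed Anticipated Risks, says that placing an epidural lead "may expose the patient to risks of epidural hemorrhage, hematoma, infection, spinal cord compression, and/or paralysis". Later in the same section it says that "if they do occur, serious adverse events will be reported to the PI, medical monitor, IRB, and FDA within the appropriate reporting timeframes", and the next sentence sends adverse events in general to the IRB and FDA as well.

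Other rules are scattered through section 9:
- 9.4 treats any event causing or prolonging hospitalization as a reportable unanticipated adverse device effect (UADE), unless the protocol specifically instructs otherwise.
- 9.13 sets deadlines for UADEs of 10 working days to the FDA and 5 to the IRB. It ends: "For this protocol, only directly related SAEs/UPIRTSOs will be reported to the IRB".
- 9.14 covers FDA reporting of unanticipated events only.
- 9.17.1 has the investigator report the adverse event to the IRB, without restriction.
- 9.17.4 has the investigator report to the IRB an event that could concern other subjects.

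**The concern.** The exemption names two classes, and the bracketed seriousness qualifier belongs to the second alone. The protocol never defines an expected event. The nearest test, in 9.2.4, calls an event unanticipated when it is inconsistent with the anticipated risks described in the protocol. A complication on the 1.4.2 list that behaves as described is therefore expected, even when it is serious.

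What is at stake is whether outside oversight learns of serious implant complications. Section 3.4 says that "Primary safety endpoints of the study will be oriented to adverse events that could originate from the implantation of the ES electrodes", among other sources, so these events are central to the study's safety question. Four of the eight subjects receive implanted leads. The internal review group in 9.17.1 is made up of co-investigators, and that section says only that the team is prepared to appoint an independent monitor. Reports to the IRB and FDA therefore carry much of the external oversight. Staff who follow one section would report an event that staff following another would not.

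**Working it through.** No arithmetic applies, and the plan states no figure to reproduce. The check is whether the sections give one answer for one event.

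**Step 1: can a listed risk be serious?** The criteria in 9.2.3 include life-threatening events, inpatient hospitalization and persistent or significant disability. Several items among the "risks of epidural hemorrhage, hematoma, infection, spinal cord compression, and/or paralysis" can meet at least one of them. A serious listed event is therefore possible on the protocol's own terms.

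**Step 2: is such an event expected?** Under 9.2.4 it is, if its nature, specificity, severity and frequency match the description in the protocol. Section 1.4.2 gives no incidence for any listed implant complication, so the frequency part of that test has no benchmark.

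**Step 3: apply every rule to one event.** Take a lead infection during the study that needs admission and is graded possible under 9.11. It is a listed risk, and admission makes it serious.

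| Section | To the IRB? | To the FDA? |
|---|---|---|
| 1.4.2 | Yes | Yes |
| 9 (opening) | No, if expected | No, if expected |
| 9.4 with 9.13 | Yes, as a UADE, unless section 9 counts as an instruction otherwise | Same condition |
| 9.13, last sentence | Cannot be determined | Not addressed |
| 9.14 | Not addressed | Only if unanticipated |
| 9.17.1 | Yes | Not addressed |
| 9.17.4 | Yes, if of concern to other subjects | Not addressed |

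The 9.13 entry cannot be determined because the grades in 9.11 are unrelated, remotely possible, possible, probable and definite. None of them is direct. Section 9.10 adds another criterion: events of unknown and questionable relationship are classed as device-associated for reporting.

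**Step 4: is there an order of precedence?** None is stated. Sections 1.4.2 and 9.17.1 cannot both be followed together with the literal exemption in section 9.

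**Step 5: is the event lost from the data?** No. Section 9 puts all adverse events on the case report form. Section 9.8 records all observed or volunteered events, serious or not, whatever their suspected cause. Sections 9.13 and 9.17.4 repeat the recording requirement.

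**The case against.** The best defence has three parts.

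- **Regulatory wording.** The sentence before the exemption promises reports as regulations require, so the exemption may be meant only for reports beyond those. That is plausible as intent. The text does not say so and names no recipient.
- **No serious events anticipated.** Section 1.4.2 says the team anticipates none, so it could be argued that no serious event is expected. That statement sits beside a list of anticipated risks that includes paralysis and cord compression, so it adds ambiguity. Likewise, a listed event that is worse or more frequent than described counts as unanticipated, but this protects only events that depart from the description.
- **Backstops.** Section 9.16 suspends enrollment and treatment after a probably or definitely related serious event, expected or not, and requires IRB consultation before resumption. Section 9.17.1 requires notice to the investigator within 24 hours. These reduce the risk. The 9.16 relatedness criterion does not reach an event graded possible, and neither section removes the contradiction.

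A reader might also infer more than the documents support:

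- **A distorted complication rate.** With four implants, one hidden event would turn 1/4 = 25% into 0/4 = 0%. This does not follow, because an unreported event is still recorded and still counts in the study data.
- **A conflict with 9.8.** Its threshold of at least possible relatedness applies only to serious events after the study period, so it sets no rival rule for events during the study.
- **A conflict with 9.7.3.** An event there is related "if it is possibly related to the research procedures", but this is one of three criteria that must all be met, and another is that the event be unanticipated. An expected event fails that test.
- **A certain conflict with 9.4.** Its exception may or may not point to section 9.
- **A safety endpoint made up mostly of expected events.** Section 3.4 names sources of events and does not list or count them.

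**Conclusion.** The point holds as a contradiction in the safety-reporting text. Taken literally, section 9 withholds serious, listed implant complications from the IRB and FDA, while 1.4.2 and 9.17.1 require reports. Section 9.13 uses a relatedness grade that the protocol does not define, and the bearing of section 9 on 9.4 is unclear.

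Its size is limited. It affects who is told and when; what is recorded and the study's own complication rate are unaffected. The implant complications concern the four subjects in the epidural arm, and the inconsistent rules apply to all eight. The conclusion rests on reading expected through 9.2.4 and the 1.4.2 list, which is the nearest thing to a definition in the document. Whether the text meets external regulations cannot be judged from the documents and is not claimed. The wording should be corrected.

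**What to change.** 1. In the opening of section 9, limit the exemption to expected adverse events that are not serious. Define expected by reference to the 1.4.2 list, and state that reported means sent to the IRB or FDA, with recording on the case report form unchanged.
2. In 9.13, replace direct relatedness with a threshold stated on the 9.11 grades. The documents do not settle which grade, so the sponsor must choose. The choice has to be squared with 1.4.2, which sets no relatedness condition.
3. Reconcile 1.4.2, section 9, 9.4, 9.13, 9.17.1 and 9.17.4 into one rule, best set out as a table. For each combination of seriousness, relatedness and expectedness, it should state who receives the report and by when. It needs an explicit FDA route for expected serious events: 9.13 gives an FDA deadline only for UADEs and 9.14 covers only unanticipated events, so pointing serious events to 9.13 is not enough. It should also say whether section 9 is an instruction of the kind 9.4 allows for.

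The cost is protocol wording and possibly one or two more reports in an eight-subject study.

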9.1 Unanticipated Adverse Device Event (UADE)

A UADE is any SAE that impacts the health or safety, or any life-threatening problem or death caused by, or associated with, a device if that event, problem, or death was not previously identified in nature, severity, or degree of incidence in the investigational plan or IDE application (including a supplementary plan or application), or any other unanticipated serious problem associated with a device that relates to the rights, safety, or welfare of participants.

9.2 Adverse Event (AE)

Any untoward medical occurrence of an investigational device; regardless of the causal relationship of the problem with the device or, if applicable, other study related treatment(s). The following categorization of AEs will be used:

9.2.1 Associated with the Investigational Device

There is a reasonable possibility that the AE may have been caused by the investigational device.

9.2.2 Life-threatening AE

Any AE that places the participant at immediate risk of death from the event as it occurred, excluding events where a reaction that, had it occurred in a more severe form, might have caused death.

9.2.3 Serious AE

An AE will be considered "serious" if it results in any of the following outcomes:

death

- a life-threatening AE
- inpatient hospitalization or prolongation of existing hospitalization
- a persistent or significant disability/incapacity
- a congenital anomaly/birth defect.

9.2.4 Unanticipated AE

Any AE, the nature, specificity, severity, or frequency of which is not consistent with the anticipated risks described within the clinical study protocol.

9.3 General Physical Examination Findings

At screening, any clinically significant abnormality will be recorded as a preexisting condition. At the end of the study, any new clinically significant findings/abnormalities that meet the definition of an AE will also be recorded and documented as an AE.

9.4 Hospitalization, Prolonged Hospitalization or Surgery

Any AE that results in hospitalization or prolonged hospitalization will be documented and reported as an unanticipated adverse device effect unless specifically instructed otherwise in this protocol. Any condition responsible for surgery will be documented as an AE if the condition meets the criteria for an AE.

Neither the condition, hospitalization, prolonged hospitalization, nor surgery are reported as an AE in the following circumstances:

- Hospitalization or prolonged hospitalization for diagnostic or elective surgical
 procedures for a preexisting condition. Surgery will not be reported as an outcome of
 an AE if the purpose of the surgery was elective or diagnostic and the outcome was
 uneventful
- Hospitalization or prolonged hospitalization for therapy of the target disease of the study, unless it is a worsening or increase in frequency of hospital admissions as judged by the clinical investigator

9.5 Post-study AE

All unresolved AE will be followed by the PI until the AE is resolved, the participant is lost to follow-up, or the AE is otherwise explained. At the last scheduled visit, the PI will instruct each participant to report any subsequent event(s) that might reasonably be related to participation in this study. The PI will notify the institutional regulatory office of any death or AE that occurs at any time after participants have discontinued or terminated study participation and may reasonably be related to this study.

9.6 Preexisting Condition

Any preexisting conditions that do not result in exclusion during screening will be recorded as an AE if the frequency, intensity, or the character of the condition worsens.

9.7 Unanticipated Problems Involving Risk to Subjects or Others (UPIRTSO)

Any unanticipated problems or AEs that meet all of the following three criteria:

9.7.1 Serious

Serious problems or events that results in significant harm, (which may be physical, psychological, financial, social, economic, or legal) or increased risk for the subject or others (including individuals who are not research subjects). These include: (1) death; (2) life threatening AE; (3) hospitalization - inpatient, new, or prolonged; (4) disability/incapacity - persistent or significant; (5) birth defect/anomaly; (6) breach of confidentiality and (7) other problems, events, or new information (i.e. publications, DSMB reports, interim findings, product labeling change) that in the opinion of the local investigator may adversely affect the rights, safety, or welfare of the subjects or others, or substantially compromise the research data.

9.7.2 Unanticipated

Events that are not already described as potential risks in the protocol, consent document, not listed in the PI's brochure, or not part of an underlying disease. A problem or event is "unanticipated" when it was unforeseeable at the time of its occurrence. A problem or event is "unanticipated" when it occurs at an increased frequency or at an increased severity than expected, **AND**

9.7.3 Related

A problem or event is "related" if it is possibly related to the research procedures.

9.8 AE Recording

At each contact with the participant, the PI will seek information on AEs. Study participants will be routinely questioned about AE at study visits. Information on all AE will be recorded immediately in the source document, and also in the appropriate AE section of the case report form (CRF). All clearly related signs, symptoms, and abnormal diagnostic, laboratory or procedure results will be recorded in the source document.

All observed or volunteered AEs (serious and non-serious) and abnormal test findings, regardless of treatment group or suspected causal relationship to the investigational device, will be recorded in the participant's case history. For all AEs, sufficient information will be pursued and or obtained as to permit; an adequate determination of the outcome, an assessment of the casual relationship between the AE and the investigational device or, if applicable other study treatment or diagnostic product. The clinical course of each event will be followed until resolution, stabilization, or until it has been ultimately determined that the study treatment or participation is not the probable cause. Serious AEs that are unresolved at the end of the study period will be followed up to determine the final outcome. Any serious AE that occurs after the study period and is considered to be at least possibly related to the study treatment or study participation will be recorded and reported immediately.

9.9 Abnormal Clinical Testing Results

If an unexpected abnormal clinical testing result is observed, and is believed to be unrelated to participation in study-related activities, the abnormal result it will be documented as an AE and the study participant will be instructed to consult with their clinical provider to determine if additional testing is needed.

9.10 Relationship and Severity Assessment

The PI, or their delegate, will promptly review documented AEs and abnormal test findings to determine if:

- The abnormal test finding will be classified as an AE
- There is a reasonable possibility that the AE was caused by the investigational device or other study treatments
- The AE meets the criteria of serious AE

If the PI's final determination of causality is "unknown and of questionable relationship to the investigational device or other study treatments," the AE will be classified as associated with the use of the investigational device or other study treatments for reporting purposes. If the PI's final determination of causality is "unknown but not related to the investigational device or other study treatments," this determination and the rationale for the determination will be documented in the respective participant's case history.

